# 8. CRITERIA FOR EVALUATION AND ENDPOINT DEFINITION

# 8.1 Primary Endpoint

The primary endpoint is feasibility of a combination agent intervention (once-weekly self-administered intravaginal 5-FU alternating with once-weekly provider-administered imiquimod) in women with biopsy confirmed high grade cervical squamous intraepithelial lesions (i.e., CIN3 lesions and CIN2 lesions diagnosis confirmed by positive p16 immunohistochemistry staining).

Feasiblity is evaluated based on safety and tolerability of the study intervention. For safety, we will assess the number of participants experiencing the dose limiting toxicity (DLT). DLT is defined as Grade 2 or greater toxicity (or Grade 1 toxicity of any genital lesion (blisters, ulcerations, or pustules)) that is possibly, probably, or definitely related and lasts for more than 5 days. For tolerability, we will assess the number of participants who are not able to apply at least 50% of the treatment due to DLT.

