# 5.6 Dose Modification

Participants will be asked to contact the study team when experiencing a possibly related adverse event. Section 11.1.3.1 describes the assessment of the severity of an adverse event. Briefly, adverse events (except female genital AEs) will be assessed according to the grade associated with the CTCAE term. Female genital AEs will be assessed according to the NIAID DAIDS Female Genital Grading Table (FGGT) (Appendix B), rather than using CTCAE.

For a Grade 1 toxicity of any genital lesion(s) (blisters, ulcerations, or pustules), that is possibly, probably, or definitely related to the study medication, the participant will not receive applications of the study drug until the toxicity has resolved. No dose modification will be made for other Grade 1 adverse events.

For Grade 2 adverse events definitely, probably or possibly related to study agent persisting until the next scheduled agent application, the next application(s) will be omitted until toxicity is resolved to Grade 1 or less.

Participants with Grade 3 or 4 events that are definitely, probably or possibly related to the study agent will receive no further doses and be followed for resolution of adverse events. If appropriate, they should remain on-study and undergo the post-intervention biopsy.

For adverse events not considered related to study agent persisting until the next agent application, the scheduled agent application may be continued or omitted at the discretion of the study physician.

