# 13.4 Primary Objective, Endpoint(s), Analysis Plan

The primary objective of the study is to assess the feasibility of intravaginal use 5-FU and imiquimod on alternating weeks in women with biopsy confirmed high grade cervical squamous intraepithelial lesions (i.e., CIN3 lesions and CIN2 lesions diagnosis confirmed by positive p16 immunohistochemistry staining).

Feasiblity is evaluated based on safety and tolerability of the study intervention. For safety, we will assess the number of participants experiencing the dose limiting toxicity (DLT). DLT is defined as Grade 2 or greater toxicity (or Grade 1 toxicity of any genital lesion (blisters, ulcerations, or pustules)) that is possibly, probably, or definitely related and lasts for more than 5 days. For tolerability, we will assess the number of participants who are not able to apply at least 50% of the treatment due to DLT.

The proportion of participants experiencing DLT and the proportion of tolerable participants will be reported along with their 95% confidence intervals. We plan to accrue at least 12 participants to evaluate the feasibility of the intervention to determine whether this intervention is worth exploring further in a subsequent trial. If  $\geq 33\%$  experience DLT, we will not proceed with further exploration using the combined agent intervention.

In the prior trial conducted by [name], self-administration of 5FU once every two weeks for a total of 16 weeks did not result in adverse events that were Grade 2 or higher. Addition of imiquimod in alternating weeks to the 5FU alone treatment may increase the type or severity of the adverse events than those observed with 5FU alone. Nevertheless, our proposed intervention is expected to have an improved safety profile than prior trials of intravaginal imiquimod because of the less frequent dosing of imiquimod employed in our trial. Therefore, we do not expect to observe a toxicity rate of greater than 30% with our study intervention.

The probabilities of observing DLT in 33% or more participants for toxicity rates no greater than 30% are listed below:

 	
Projected toxicity rate	Probability of observing DLT in
	≥ 33% participants
≤ 5%	< 1%
10%	2.6%
20%	20.5%
30%	50.7%

The probabilities of having less than 66% tolerable participants with projected tolerability rates of 50-80% are listed below:

Projected tolerability rate	Probability of < 66% tolerable participants
80%	7.3%

70%	27.6%
60%	56.2%

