#### DIVISION OF AIDS TABLE FOR GRADING THE SEVERITY OF ADULT AND PEDIATRIC ADVERSE EVENTS PUBLISH DATE: DECEMBER 2004

Addendum 1

Female Genital Grading Table for Use in Microbicide Studies

INDIVIDUAL SIGNS/SYMPTOMS								
PARAMETER	GRADE 0 NORMAL	GRADE 1 MILD	GRADE 2 MODERATE	GRADE 3 SEVERE	GRADE 4 POTENTIALLY LIFE- THREATENING			
GENERAL								
Odor	No complaint	Mild-moderate unpleasant odor	Severe unpleasant odor	NA	NA			
PAIN AND TENDERNESS (Specify Area: Vulvar/Perineum, Vagina, Cervix (including cervical motion tenderness), Uterus, Adnexae, Pelvic/Lower Abdominal, or Ovulatory) *Note – if both pain and tenderness are present, only report the one with the most severe grade								
Pain * 1	None	Pain causing no or minimal interference with usual social & functional activities	Pain causing greater than minimal interference with usual social & functional activities or the need for non-narcotic medication	Pain causing inability to perform usual social & functional activities or the need for narcotic medication	Disabling pain causing inability to perform basic self- care functions OR hospitalization (other than emergency room visit) indicated			
Tenderness* 1	None	Mild tenderness	Moderate tenderness	Severe tenderness	NA			
Dyspareuni a (pain w ith sexual activity)	None	Pain causing no or minimal interference with sexual function	Pain causing greater than minimal interference with sexual function	NA	NA			
Dysmenorrhea/cra mping with menses	None	Pain causing no or minimal interference with usual social & functional activities	Pain causing greater than minimal interference with usual social & functional activities or the need for non-narcotic medication	Pain causing inability to perform usual social or functional activities or the need for narcotic medication	NA			

 If pain or tendemess is included in the grading of another category (e.g., PID), it should not be graded again in the pain or tendemess

category.

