#### DIVISION OF AIDS TABLE FOR GRADING THE SEVERITY OF

ADULT AND PEDIATRIC ADVERSE EVENTS

PUBLISH DATE: DECEMBER 2004

Addendum 1

Female Genital Grading Table for Use in Microbicide Studies

INDIVIDUAL SIGNS/SYMPTOMS								
PARAMETER	GRADE 0 NORMAL	GRADE 1 MILD	GRADE 2 MODERATE	GRADE 3 SEVERE	GRADE 4 POTENTIALLY LIFE- THREATENING			
GENITOURINARY SIGNS/SYMPTOMS - VULVA								
∨ulvar/vaginal itching	None	Itching causing no, mild, or moderate interference with usual social & functional activities	Itching causing inability to perform usual social & functional activities; may require intervention such as antihistamine or bathing to provide relief	NA	NA			
∨ulvar edema	None	Mild, non-pitting edema	Moderate, 1-2+ pitting edema	3+ pitting edema, severe enough to require urinary drainage, or w eeping edema ± skin breakdow n	NA			
Vulvar erythema	None	Erythema covering < 50% of vulvar surface	Erythema covering ≥ 50% of vulvar surface	NA	NA			
Vulvar lesions (findings seen only by colposcopy should not be included here)	Normal variants including skin tags, moles, scars, etc.	Blisters, ulcerations, or pustules - no treatment indicated	Blisters, ulcerations or pustules, with treatment indicated	Severe epithelial disruption with hospitalization indicated	NA			
Vulvar rash	None	Rash covering < 50% of vulvar surface	Rash covering ≥ 50% of vulvar surface	Severe epithelial disruption with hospitalization indicated	NA			
Bartholin's or Skene's gland	No findings	Cyst with no inflammation	Cyst or abscess with outpatient intervention indicated	Cyst or abscess with hospitalization indicated	Necrotizing fasciitis from Bartholin's abscess			
GENITOURINARY SIGNS/SYMPTOMS – VAGINA ** Note – if vaginal discharge is present both by history and on examination, only report the one with the most severe grade								
Vaginal edema	None	Mild-moderate engorgement	Loss of ruggae and friability	NA	NA			
∨aginal erythema	None	Erythema covering < 50% of vaginal	Erythema covering ≥ 50% of vaginal	NA	NA			

surface

surface

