#### DIVISION OF AIDS TABLE FOR GRADING THE SEVERITY OF

ADULT AND PEDIATRIC ADVERSE EVENTS

PUBLISH DATE: DECEMBER 2004

Addendum 1

Female Genital Grading Table for Use in Microbicide Studies

INDIVIDUAL SIGNS/SYMPTOMS							
PARAMETER	GRADE 0 NORMAL	GRADE 1 MILD	GRADE 2 MODERATE	GRADE 3 SEVERE	GRADE 4 POTENTIALLY LIFE- THREATENING		
∨aginal dryness	No complaint	Dryness causing no or minimal interference with usual sexual, social, & functional activities	Dryness causing greater than minimal interference with usual sexual, social, & functional activities	NA	NA		
Vaginal discharge by participant report **	Participant's usual amount of discharge, regardless of color or quantity	Mild-moderate increase in amount above participant baseline - no sanitary protection required	Profuse increase in discharge requiring pad use or other hygienic intervention	NA	NA		
Vaginal discharge as observed by clinician ** (red or brow n discharge should be reported under bleeding, not discharge)	Slight amount of discharge, any color	Mild-moderate increase in amount	Significant increase in amount with pooling in vagina on examination	NA	NA		
Vaginal abrasions or lacerations (including probable applicator injuries)	None	Superficial disruptions and disruptions extending through the mucosa with minimal impact on life	Large disruptions extending through the mucosa or large superficial disruptions, hospitalization not indicated	Large disruptions extending through the mucosa or large superficial disruptions, hospitalization indicated	Lacerations extending into the peritoneal cavity, bladder, or rectum		
Vaginal lesions (findings seen only by colposcopy should not be included here)	Normal variants including skin tags, moles, scars, etc.	Blisters, ulcerations, or pustules, no treatment indicated	Blisters, ulcerations, or pustules with treatment indicated	Severe epithelial disruption requiring hospitalization	NA		
Vaginal and Cervical masses (polyps, myomas, or possible malignancy)	None or normal variants such as Nabothian cyst or Gartner duct cyst	Polyp or myoma or undiagnosed mass without symptoms	Polyp, myoma, or undiagnosed mass causing mild symptoms, e.g., bleeding/pain not requiring more than mild analgesia	Polyp, myoma, or undiagnosed mass causing severe symptoms, e.g., bleeding/pain affecting bladder and bow el function	∨isible cervical cancer		
GENITOURINARY	SIGNS/SYMPTOM	S-CERVIX					
Cervical edema and friability	None	Edema without friability	Friable cervix	NA	NA		

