#### DIVISION OF AIDS TABLE FOR GRADING THE SEVERITY OF ADULT AND PEDIATRIC ADVERSE EVENTS PUBLISH DATE: DECEMBER 2004

Addendum 1

COMPOSITE SIGNS/SYMPTOMS (Use instead of individual categories if 2 or more signs/symptoms are present)							
PARAMETER	GRADE 0 NORMAL	GRADE 1 MILD (Use if all signs/ symptoms would indiv idually be Grade 0 or 1)	GRADE 2 MODERATE (Use if one or more signs/symptoms would indiv idually be Grade 2 and all others Grade 0 or 1)	GRADE 3 SEVERE (Use if one or more signs/symptoms would indiv idually be Grade 3)	GRADE 4 POTENTIALLY LIFE- THREATENING		
NO ORGANISM ID	ENTIFIED BUT INA	DEQUATE TESTIN	G PERFORMED				
Vulvovaginitis (combinations of pain, itching, erythema, edema, rash, tenderness, or discharge)	None	Mild signs/ symptoms	Moderate signs/ symptoms	Severe signs/ symptoms	NA		
Cervicitis (combinations of dyspareunia, erythema, edema, tenderness, and discharge)	None	Mild signs/ symptoms	Moderate signs/ symptoms	Severe signs/ symptoms	NA		
PID (if Gonorrhea or Chlamydia identified use that category)	None	NA	Cervicitis with mild uterine tenderness, ± mild cervical motion tenderness, no signs of peritoneal irritation	More diffuse tenderness, any signs of peritoneal irritation, or indications for hospitalization	Tubo-ovarian abscess or surgery required for resolution		
NO ORGANISM ID	ENTIFIED AFTER A	PPROPRIATE TES	TING PERFORMED	þ			
Vulvovaginitis (combinations of pain, itching, erythema, edema, rash, tenderness, or discharge)	None	Mild signs/ symptoms	Moderate signs/ symptoms	Severe signs/ symptoms	NA		
Cervicitis (combinations of dyspareunia, erythema, edema, tenderness, and discharge)	None	Mild signs/ symptoms	Moderate signs/ symptoms	Severe signs/ symptoms	NA		
PID (if Gonorrhea or Chlamydia identified use that category)	None	NA	Cervicitis with mild uterine tenderness, ± mild cervical motion tenderness, no signs of peritoneal irritation	More diffuse tenderness, any signs of peritoneal irritation, or indications for hospitalization	Tubo-ovarian abscess or surgery required for resolution		

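### A related Grade 3–4 toxicity of 5 days or less that ends treatment under section 5.6 can be left out of the DLT count

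*Combined protocol and SAP*

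**What the plan says.** Sections 8.1 and 13.4 give the same definition. A DLT is a toxicity of Grade 2 or higher, or a Grade 1 genital lesion (given in parentheses), "that is possibly, probably, or definitely related and lasts for more than 5 days". Neither section makes an exception for Grade 3–4 or treats a permanent stop as a DLT in itself.

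Tolerability, the other half of the primary endpoint, counts women "not able to apply at least 50% of the treatment due to DLT".

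Section 5.6 governs dosing and has no duration test at the top grades: "Participants with Grade 3 or 4 events that are definitely, probably or possibly related to the study agent will receive no further doses". At Grades 1 and 2 it only holds or omits applications.

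The decision rule is in 13.4. If at least 33% "experience DLT, we will not proceed with further exploration using the combined agent intervention". No rule is attached to the tolerability count.

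**The concern.** Grade 3–4 is the level at which the protocol ends a woman's treatment for good. An endpoint named for dose-limiting toxicity would be expected to include the toxicities that do this, but the duration condition can exclude them. Because tolerability counts only shortfalls caused by a DLT, the same woman can drop out of both halves of the primary endpoint.

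At stake are the reported DLT proportion and the single pre-specified no-go trigger. With 12 to 14 women, that trigger can turn on one person. The event itself would not be hidden: it would still appear in the adverse event tables (13.7), any serious adverse event report (11.2) and the monitoring board's review (12.4).

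**Working it through.** **1. Scope of the duration condition.** In 8.1 and 13.4 the words on relatedness and duration come after the Grade 1 parenthesis has closed, so they qualify the whole phrase. Confining the duration condition to Grade 1 would also confine the relatedness condition to Grade 1, and unrelated Grade 2 or higher events would then be DLTs. That cannot be intended.

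**2. Who is missed.** She has a related Grade 3–4 event that ends within 5 days, and no other related Grade 2 or higher toxicity or Grade 1 genital lesion lasting longer.
- On an onset-to-end count, a Grade 3 event that fades through lower grades past day 5 still counts.
- The genital grading table in Appendix B has a composite category, with the instruction "Use instead of individual categories if 2 or more signs/symptoms are present". Vulvovaginitis with several signs is therefore one event and counts if it persists as a whole.
- Grade 3 can be met without a long course. For pain it is "Pain causing inability to perform usual social & functional activities or the need for narcotic medication". CTCAE-graded systemic events can also reach it.
- If she had received 3 or fewer of the 8 initiation-phase applications (under 50%), she is also outside the tolerability count. If she was stopped later, tolerability is unaffected.

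**3. The plan's own figures.** The rule is met at 4 or more of 12 (4/12 = 33.3%; 3/12 = 25.0%). With X ~ Binomial(12, p), P(X ≥ 4) is 0.22%, 2.6%, 20.5% and 50.7% at p = 5%, 10%, 20% and 30%. This matches the table in 13.4 (below 1%, 2.6%, 20.5%, 50.7%). The arithmetic there is right; the question is which events enter X.

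**4. Effect of one uncounted woman.** With n = 12 she changes the outcome only if exactly 3 of the other 11 are DLTs: C(11,3) p³(1−p)⁸. With n = 14 the threshold is 5 (5/14 = 35.7%; 4/14 = 28.6%), so exactly 4 of the other 13 are needed: C(13,4) p⁴(1−p)⁹.

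| DLT rate in the others | n = 12 | n = 14 |
|---|---|---|
| 5% | 165 × 0.05³ × 0.95⁸ = 1.4% | 715 × 0.05⁴ × 0.95⁹ = 0.3% |
| 10% | 165 × 0.1³ × 0.9⁸ = 7.1% | 715 × 0.1⁴ × 0.9⁹ = 2.8% |
| 20% | 165 × 0.2³ × 0.8⁸ = 22.1% | 715 × 0.2⁴ × 0.8⁹ = 15.4% |
| 30% | 165 × 0.3³ × 0.7⁸ = 25.7% | 715 × 0.3⁴ × 0.7⁹ = 23.4% |

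These figures are conditional on one such woman and assume nothing about how often she occurs.

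**5. Illustration with an assumed frequency.** Let a further share q of women have only a brief related Grade 3–4 event. The documents give no value for q; 1% and 5% are assumptions. Counting these women gives a no-go probability of P(Binomial(12, p+q) ≥ 4). The reconciled count is never below the as-written count, so the difference is the chance of a changed decision.

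| DLT rate as written | No-go as written | No-go, q = 1% (change) | No-go, q = 5% (change) |
|---|---|---|---|
| 10% | 2.6% | 3.5% (0.9%) | 9.2% (6.7%) |
| 20% | 20.5% | 23.3% (2.7%) | 35.1% (14.6%) |

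Changes are taken before rounding.

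**The case against.** **Different purposes.** Section 5.6 protects one woman and the DLT count judges the regimen, so they need not share a threshold. The definition already reaches down to Grade 1 lesions, with persistence as its filter. This is a fair account of why the sections differ, and they do not formally contradict each other. It does not explain why a toxicity that permanently ends dosing should fall outside the count.

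**Narrow case.** Much of the Grade 3 list is unlikely to be over in 5 days. Vulvar lesions and rash need "Severe epithelial disruption with hospitalization indicated", and vaginal lesions need "Severe epithelial disruption requiring hospitalization". Vaginal erythema, vaginal edema, discharge, itching and visible cervical lesions have no Grade 3 at all. The protocol reports no Grade 2 or higher events in the earlier 5-FU trial (13.4), and no stopping for side effects in one imiquimod trial (6.2). All of this stands and limits the weight of the point. Against it, section 2.3 acknowledges that safety data on combining agents on the cervix are lacking.

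**Limited consequence.** At a 5% DLT rate one such woman changes the decision only 1.4% of the time. The rule is also one-sided, since a result below 33% does not oblige anyone to proceed. Both remarks are correct.

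**Late and partial change.** The document is at Amendment 11 of an open, single-arm study, so redefining the endpoint could happen with outcomes known. Reporting both counts answers that. A woman who stops under 8.3 after a brief Grade 2 event would still be uncounted. That is a true limit of the proposal, which addresses only the stop that 5.6 makes mandatory.

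**Conclusion.** The concern holds. Followed exactly, the plan can leave a treatment-ending toxicity out of the DLT proportion and, where under half the applications were received, out of the tolerability count as well. No other section repairs this.

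The gap is narrow, but it lies in the primary endpoint and its only numeric trigger. For n = 12 and DLT rates of 10% to 30% in the other women, one such case decides the outcome with probability 7.1% to 25.7%; at 5% it is 1.4%. Any unconditional figure depends on a frequency the documents do not give. The reading of the text is secure; how often the case arises is unknown. It should be fixed because the correction is cheap, not because a large effect has been shown.

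**What to change.** Reconcile 8.1 and 13.4 with the existing 5.6, for endpoint counting only:
- Count a related toxicity that leads to permanent discontinuation under 5.6 as a DLT whatever its duration.
- Count that woman as a tolerability failure when she received less than 50% of applications.
- Keep the more-than-5-days condition for all other events.
- In the same edit, state whether the 5 days run from onset to resolution or at the qualifying grade. This is a clarification and the point does not rest on it.
- If data already exist, report the count as written and the reconciled count side by side.

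Dosing and clinical management in 5.6 do not change.

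The cost is one or two sentences in each section, plus the sponsor and IRB approval that 14.3 requires for an amendment. Grade, attribution, onset date and end date are already collected (11.1.2), so an onset-to-resolution count needs no new data. Counting days at the qualifying grade would need grade changes to be dated. The downside is a possibly higher DLT rate and a somewhat higher chance of no-go: with n = 12 and a 20% DLT rate, from 20.5% to 23.3% if a further 1% of women are affected, or to 35.1% if a further 5% are (assumed rates).

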# 8.2 Secondary Endpoints

- 8.2.1 Response to the combination of agent intervention on cervical disease regression (endpoint based on histologic regression from high-grade lesions to low-grade- or no lesions and clearance of high risk-HPV detection) between baseline and study exit visits.
- 8.2.2 Effect of the combination agent intervention on genotype-specific HPV clearance between baseline and study exit visits.
- 8.2.3 Effect of the combination agent intervention on biomarkers of local immune activation (measurement of changes in expression of Toll-like receptors (TLR2, TLR 3, TLR7, TLR8 and TLR9) and T-regulatory cells (Foxp3) and the levels of mRNA expression and the innate (IFN-α2), immune mediating (IFN-Y, IL-10, IL-12), and proinflammatory (IL-1α, -1β, -6, -8, MIP-1α, TNF) cytokine with intravaginal 5-FU and imiquimod between baseline and study exit visits.

The study will also collect specimens for exploratory studies of vaginal microbiome, proteomics and metabolomics to identify factors affecting histologic regression, HPV clearance and immune activation.

# 8.3 Off-Agent Criteria

Participants may stop taking study agent for the following reasons: completed the protocol-prescribed intervention, AE or serious adverse event (SAE), inadequate agent supply, noncompliance, concomitant medications, medical contraindication. Participants will continue to be followed, if possible, for safety reasons and in order to collect endpoint data according to the schedule of events.

# 8.4 Off-Study Criteria

Participants may go 'off-study' for the following reasons: the protocol intervention and any protocol-required follow-up period is completed, AE/SAE, lost to follow-up, non-compliance, concomitant medication, medical contraindication, withdraw consent, death, determination of ineligibility (including screen failure), pregnancy.

